The Impact of Comorbid Chronic Pain on Older Adults Depression and Treatment of Behavioral Activation: A Nested Qualitative Sub-Study of Participants in the BASIL+ Trial

PROTOCOL (IRAS PROJECT ID 293203)

Version 1.2

Teesside University/ University of York

School of Health & Life Sciences/ Department of Health Sciences

Teesside University/ University of York

[name]

Version Date: 09/12/2022

Author: [name]

Chief Investigator: [name]

Supervisors: [name], [name] & [name]

Collaborator: [name]

This study will form part of a National Institute of Health and Care Research (NIHR) North East North Cumbria Applied Research collaboration (NENC ARC) funded doctoral research study undertaken by a collaborator of the BASIL⁺ team ([name] (AC)). This work will be led by AC with support from other members of the BASIL⁺ team.

Chronic Pain, also known as persistent pain, is characterised by pain which has continued for more than 3 months (1). Chronic pain affects approximately 50-60% of UK older adults (2) and often coexists with depression (3, 4, 5). This comorbid indication affects approximately 13% of older adults (6). Pain interference in everyday life increases with age (7) and the combination of experiencing both conditions leads to poorer health outcomes and overall functioning than experiencing either condition alone (4). The literature on the impact of pain on depression outcomes has been steadily rising. Patients who suffer from depression with comorbid pain report significantly lower benefits, including less relief from depressive symptoms when taking antidepressant medication(8) and limited the effectiveness of a US collaborative care trial for older adults with depression which incorporated problem-solving therapy and antidepressant medication (9). Together, these findings suggest that pain may be a potential barrier to depression treatment. It is unknown, however, how comorbid chronic pain impacts patients' engagement in collaborative care and more specifically brief psychological therapy such as behavioural activation (BA). The BASIL⁺ trial will provide an opportunity to explore this qualitatively. This sub-study will aim to explore if chronic pain impacts patients' depression and treatment.

In-depth, semi-structured interviews of a sub-sample of BASIL⁺ participants will be conducted. Potentially eligible participants will include existing BASIL⁺ participants (those participants who have not yet completed their 12 month follow-up) and those BASIL⁺ participants who have completed their 12 month follow up, who were randomised to the BA intervention and who expressed experiencing pain as defined as a response of "moderate, quite a bit or extremely" on question 8 of the SF-12 at baseline ("During the past 4 weeks, how much did pain interfere with your normal work (including work outside the home and housework?)") and/or responded as having "moderate or extreme pain or discomfort" on question 4 of the EQ-5D at baseline ("Please indicate which statements best describe your own health state today: I have no pain or discomfort, I have moderate pain or discomfort, I have extreme pain or discomfort"). This will indicate that these BASIL⁺ participants were experiencing some level of pain at study entry. These baseline data will be provided to AC by the BASIL⁺ statisticians. No other member of the BASIL⁺ team will have access to these baseline data

Eligibility for this sub-study will be confirmed by AC. This will involve asking potentially eligible BASIL⁺ participants two telephone screening questions which will assess how often participants have pain and how pain limits their life/work activities in the last three months. This will confirm the presence or absence of chronic pain (10). Participants who respond as "never" or "some days" to question 1 ("In the past three months, how often did you have pain?") will be ineligible for the sub-study as chronic pain is absent. These BASIL⁺ participants will be thanked for their time and, where appropriate, will be reminded

that a researcher will be in contact for their 12-month follow-up. Participants who respond as “most days” or “everyday” to question 1 will be eligible and will be asked the second question (“Over the past three months how often did pain limit your life or work activities?”). Participants who respond as “never” or “some days” will be graded as having mild/bothersome chronic pain; those who respond as “most days” or everyday will be graded as having high impact chronic pain. For those BASIL+ participants where presence of chronic pain is indicated, the BASIL+ statisticians will provide AC with participants' details to inform the sampling framework (to include participant ID, age, gender, ethnicity, PHQ9 baseline scores, EQ-5D baseline scores, SF-12 baseline scores, postcode (for deprivation indices) and BA ‘treatment response’ (categorised as either a ‘favourable’ or ‘(non) favourable’ response). To define a ‘favourable’ or ‘(non) favourable’ response to the BA treatment, a reliable change index of 0.5 SD between participant's PHQ9 scores at screening/baseline and three month post-randomisation (primary outcome measure) will provide the best opportunity to identify participants who have responded favourably and ‘(non) favourably’ to the BASIL+ BA intervention. The change index will provide a general idea of how participants responded to the BA intervention which will be discussed further in the sub-study interview. The above data will be provided to AC by the BASIL+ statisticians. No other member of the BASIL+ team will have access to these data.

Approximately 10 participants will be recruited initially. If after the initial recruitment round new themes are still arising, then further rounds of recruiting three participants at a time will be conducted until no new pertinent themes are arising, or unless no eligible participants remain to be approached. Participants will not be approached about this sub-study until completion of their BASIL+ primary outcome assessment (at 3 months post-randomisation).

The existing BASIL+ participant information sheet advises participants that they may be approached to provide their feedback on their experiences of taking part in the BASIL+ study (see section 4.5). The BASIL+ team will provide AC with a list of BASIL+ participants who were randomised to the intervention and who have either not yet completed their 12 month follow up (existing BASIL+ participants) or who have completed their 12 month follow up. This list will include only those BASIL+ participants who provided their consent to participate in a qualitative interview as part of the BASIL+ study (as outlined in section 4.5). For those participants who have completed their 12 month follow up, the eligible participant list will include only those participants who also provided their consent (as part of their consent to join BASIL+) to be contacted (by the BASIL+ team) about future related studies.

In addition, participants who took part in or have been approached for the BASIL+ qualitative study (see section 4.6) or the therapeutic alliance sub-study (see section 4.15) will not be approached for this chronic pain sub-study and will be removed from the eligible participant list. Equally, any participants invited to or who participate in this sub-study will be relayed back to the BASIL+ qualitative team and ER so they are not approached for their

respective qualitative studies. This will ensure no participants are contacted for more than one qualitative study and, therefore, reduce any further participant burden

AC will contact potential participants by telephone to invite them to provide their feedback on the sub-study and how their potential pain impacted their depression and experience of the 'BA Support' (BA intervention) in the BASIL⁺ study. If participants are interested, verbal consent to screen for confirmation of chronic pain will be received and recorded. Participants who do not wish to answer these questions will be thanked for their time and will not complete an interview. AC will ask participants in the last three months how often they have had pain and how often pain limited life or work activities(10). Participants whose responses to these questions indicate the presence of chronic pain will be asked if they would like to take part in this sub-study.

For those participants who meet the sub-study criteria and are willing to complete an interview, AC will confirm a date and time suitable for the participant to have the interview and the participant's preferred method of meeting either by telephone or via an approved virtual platform. Verbal consent for each participant will be received before the interview commences and will be audio recorded (as detailed in section 4.13). The interview should last approximately 45 minutes. Where real or potential risk is identified during the interviews AC will follow all appropriate and robust BASIL⁺ risk protocols (see section 6.6 for risk management).

All interviews will be digitally recorded (with participant consent) on an encrypted Dictaphone (or any other approved method), anonymised and transcribed. Transcription of the audio recordings will be completed by AC or via an approved transcription service. The transcripts will form the data for analysis. The audio recordings and any electronic transcriptions will be stored securely on password-protected secure servers at the University of York with access limited as relevant to the delivery of this sub-study. The interview topic guide has been developed in consultation with the BASIL⁺ team, AC's PhD supervisors (experts in chronic pain, behavioural activation, and qualitative methodology). The topic guide will be piloted with the first two participants and amended iteratively if required.

Thematic analysis (based on Braun and Clarke (11, 12) will be used to analyse the data to understand the nature of people's experiences (i.e phenomenology). Codes will be generated from the transcripts which will form themes, these themes will be reviewed, defined, and reported.

This chronic pain sub-study forms part of AC's doctoral research. A quantitative effect modification study is being undertaken simultaneously based on data from three of the largest BA trials in the UK (CASPER (13), CASPER+ (14) and SHARD (15)) in a mixed-methods design. The results of these two studies together will indicate to what extent pain impacts depression and potentially identify sub-groups of individuals in which BA is less effective. This will inform the next stage of this doctoral research which will continue under the wider MODS programme of research.

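### Does calling a 0.5 SD change in PHQ9 a reliable change index make the favourable-response label unfit for sampling?

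*Protocol*

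**What the plan says.** The point lies in the protocol's unnumbered paragraphs on eligibility and the sampling framework. Once screening has indicated chronic pain, the BASIL+ statisticians pass the sub-study researcher a set of descriptors. These include "PHQ9 baseline scores, EQ-5D baseline scores, SF-12 baseline scores", demographic details, postcode, and a treatment response that is "categorised as either a ‘favourable’ or ‘(non) favourable’ response".

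Response is defined by "a reliable change index of 0.5 SD between" the participant's "PHQ9 scores at screening/baseline and three month post-randomisation". The protocol says that this "will provide the best opportunity to identify participants who have responded favourably and" those who have not. It then limits the claim: "The change index will provide a general idea of how participants responded to the BA intervention", and response is to be taken up again at interview.

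No reliability coefficient, confidence level or source for the SD is given. Initial recruitment is about 10, with further rounds of three. The paragraph on transcription makes the transcripts the data for analysis, and the method is thematic analysis.

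**The concern.** A reliable change index compares an observed change with the change that measurement error alone could produce, so it needs the reliability of the scale. Half an SD is a fixed fraction that ignores reliability. The phrase therefore joins two rules that can classify the same person differently, and the name promises a protection against measurement error that the figure may not give.

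Three details are also open. The SD could be that of baseline scores or of change scores. The start score could be the screening or the baseline PHQ9. The (non) favourable group combines unchanged and worsened participants, and the listed descriptors do not expressly include a three-month score that would separate them.

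This is the only outcome-based item among the descriptors. If it sorted people badly, a sample of about 10 could hold an unintended mix of responders, or contain no one who worsened.

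**Working it through.** **Inputs.** From the protocol: a cut of 0.5 SD on PHQ9 change to three months. Assumed, because the protocol gives none: reliability r of 0.70 to 0.95; confidence levels of 95%, 90% and 80%; normal errors, equal variances and no systematic shift. The 0.5 SD figure cannot be reproduced as a reliable change threshold, because the protocol gives no inputs for one.

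**Step 1: reliable change in SD units.** The SE of a difference is s = sqrt(2(1 − r)), and the threshold is z × s, with z = 1.96, 1.645 or 1.2816. For example, at r = 0.80, s = sqrt(0.40) = 0.632 and 1.96 × 0.632 = 1.24.

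| r | s | 95% | 90% | 80% |
|---|---|---|---|---|
| 0.70 | 0.775 | 1.52 | 1.27 | 0.99 |
| 0.80 | 0.632 | 1.24 | 1.04 | 0.81 |
| 0.90 | 0.447 | 0.88 | 0.74 | 0.57 |
| 0.95 | 0.316 | 0.62 | 0.52 | 0.41 |

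Setting z × s = 0.5 gives r = 1 − (0.5/z)²/2, which is 0.967 at 95%, 0.954 at 90% and 0.924 at 80%. The mismatch between name and figure is real at the conventional level, although the protocol never claims 95%.

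**Step 2: errors under each rule.** For a participant with no true change, P(favourable) = 1 − Φ(0.5/s) under the 0.5 SD cut, and 2.5% under a 95% index. For a participant with a true improvement of 1 SD, P((non) favourable) = Φ((0.5 − 1)/s) under the 0.5 SD cut, and Φ(1.96 − 1/s) under a 95% index.

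| r | No change, labelled favourable: 0.5 SD | Same: 95% index | True 1 SD gain, labelled (non) favourable: 0.5 SD | Same: 95% index |
|---|---|---|---|---|
| 0.70 | 26% | 2.5% | 26% | 75% |
| 0.80 | 21% | 2.5% | 21% | 65% |
| 0.90 | 13% | 2.5% | 13% | 39% |
| 0.95 | 6% | 2.5% | 6% | 11% |

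Against a true gain of 1 SD, the 0.5 SD cut lies midway and balances the two errors. The 95% index guards against one error at a large cost in the other. When the aim is to find some participants of each kind to interview, the balanced cut is the more useful one.

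**Step 3: the unnamed SD.** Half the SD of change, in baseline SD units, is 0.5 × sqrt(2(1 − ρ)). For an assumed baseline to three-month correlation ρ of 0.3, 0.5 or 0.7 this is 0.59, 0.50 or 0.39. With an illustrative baseline SD of 5 points, the cuts are 3.0, 2.5 and 1.9 points. PHQ9 scores are whole numbers, so the working cuts are 3, 3 and 2. Half the baseline SD is 2.5 points, a working cut of 3. The choice of SD thus moves the cut by at most one point in this example.

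**Step 4: where the label goes.** Eligibility rests on baseline pain items, two telephone questions and consent. No quota by response is stated. The analysis uses transcripts only, and no comparison of favourable with (non) favourable participants is planned.

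**The case for a change.** The best case for a change is that the protocol sets this rule itself, so the misnomer cannot be put down to detail held elsewhere. The statisticians apply the rule and the researcher uses the result, so the definition should be clear to both. With about 10 interviews, a few misplaced participants could alter the mix, and interviews cannot reveal worsened participants who were never approached. The protocol also says that this study and a parallel quantitative study will together help to identify groups in whom the therapy works less well, which makes non-response relevant. The remedy would be only a paragraph of wording and one extra flag.

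The naming error stands. The rest carries less weight:

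- Renaming the rule while keeping 0.5 SD reclassifies no one.
- One group derives the label for everyone, from data in which the SD is known, so a consistent choice is likely. The descriptor list names the baseline PHQ9, which points to the start score.
- The descriptor list is not clearly exhaustive, and the statement that the data above will be supplied follows the mention of three-month scores. The researcher may therefore receive them, and the statisticians hold them in any case.
- A split of unchanged from worsened would be descriptive. With about 10 initial interviews it would hardly work as a stratum.
- The quantitative arm of the mixed-methods work uses three other trials and does not depend on this label.
- The best sorting tool to hand can still give only a general idea, so those two statements do not conflict. Nor does the protocol say that anyone will be reported as reliably changed.

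**Conclusion.** The concern is right about terminology: a fixed 0.5 SD cut is not a reliable change index, and it falls short of 95% reliable change for any reliability below about 0.967. It does not justify a change to the plan. The cut itself is a fair trade-off for purposive sampling. On the assumed reliabilities of 0.70 to 0.95 its two error rates are equal, at 26% to 6%, whereas a 95% index would miss 75% to 11% of participants with a true 1 SD gain. The SD and start score are gaps that the BASIL+ statisticians would fill sensibly, with a spread of about one PHQ9 point in the example worked.

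These magnitudes rest on assumed reliability, SD and correlation, and the share of participants with no true change is unknown. The conclusion does not depend on them. The label sets no eligibility, feeds no test or comparison and is revisited at interview, so following the protocol as written would not lead to a wrong conclusion. The phrase should simply be read as a 0.5 SD change threshold.

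### The telephone invitation presupposes that pain had an effect, which the stated aim leaves open, so people who feel it made no difference may be under-represented

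*Protocol*

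**What the plan says.** The protocol's sections are unnumbered, so places are given by content.

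- **Background and aim (opening section).** The aim is stated as "This sub-study will aim to explore if chronic pain impacts" patients' depression and treatment. Just before it, the knowledge gap is worded differently: "It is unknown, however, how comorbid chronic pain impacts" patients' engagement in collaborative care and brief psychological therapy.
- **Recruitment by telephone.** The researcher calls potential participants and invites them "to provide their feedback on the sub-study and how their potential pain impacted their depression and experience of the" BA Support. The next step is conditional on interest: "If participants are interested, verbal consent to screen for confirmation of chronic pain will be received and recorded". People whose answers "indicate the presence of chronic pain will be asked if they would like to take part in this sub-study" then receive a second request.
- **Eligibility.** Those called were selected on baseline SF-12 question 8 and/or EQ-5D question 4, taken to show that these "participants were experiencing some level of pain at study entry". Eligibility is then settled by one frequency item, "In the past three months, how often did you have pain". A second item only grades people who are already eligible.
- **Sampling and sample size.** Once chronic pain is indicated, the statisticians supply age, gender, ethnicity, baseline scores, postcode and a favourable or (non) favourable BA response. About 10 people are recruited first, then three at a time until no new pertinent themes arise or no eligible people remain.
- **Use of results.** The findings are to be read with a quantitative effect modification study of three trials, to indicate how far pain affects depression.

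**The concern.** A study that asks whether pain matters needs to hear from people for whom it did not. An invitation to talk about how pain affected someone's depression and therapy suits people who believe that it did. Someone who has pain but sees no link to mood or to BA may reasonably conclude that they have nothing to contribute, and decline.

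If that happens, the accounts that say no are missing before any data are collected. This matters more here than in a purely descriptive study, because the results are meant to feed a statement about the extent of pain's impact and to inform the next stage of the research.

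**Working it through.** No arithmetic applies: the sub-study has no effect size, error rate or calculated sample size. The check is a comparison of the protocol's statements, followed by a search for any later step that would reveal or repair the loss.

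1. **Does the invitation presuppose an effect?** The aim uses 'if'. The invitation uses 'how' with the past tense 'impacted', and its only hedge, 'potential', is attached to pain. As described, it allows that a person may have no pain, but not that the pain had no effect.

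2. **Does the invitation act as a filter?** Yes. Consent to screening is sought only from those who are interested ("If participants are interested, verbal consent to screen for confirmation of chronic pain will be received and recorded"). The second request, after the screen, reaches only people who passed this point, so it cannot bring back those who left at it.

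3. **Would the sampling framework correct the loss?** No, for two reasons. Its data are supplied only after a positive screen, so treatment response is not supplied for people who decline at the invitation. And no item records whether the person thinks pain affected their depression or BA. SF-12 question 8 concerns interference with normal work, and the second screening item concerns limits on life or work activities. BA response gives spread in outcome, not in perceived pain impact.

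4. **Would the stopping rule detect it?** No. Recruitment ends when no new pertinent themes arise among those interviewed. If people who saw no impact tend not to enter, themes can run out without them.

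5. **Would those people be heard elsewhere?** Not in the other two qualitative studies. Anyone invited to this sub-study, whether or not they take part, is reported back so that those studies do not approach them.

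6. **Can the risk be sized?** No. That would need the share of eligible people who feel pain made no difference, and how much less often they accept than the others. The protocol gives neither, and nothing in it shows that acceptance differs at all.

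**The case against.** The strongest reply is that the invitation sentence tells protocol readers what the call is for. It is not given as a verbatim script, whereas the screening questions are. The words actually spoken may be neutral. The protocol's framing is also mixed: it words the knowledge gap with 'how' ("It is unknown, however, how comorbid chronic pain impacts"), and a thematic, phenomenological analysis suits a 'how' question. These points stand and limit the finding to a risk. They do not remove it, because this sentence is the only text shown on how the purpose is put to participants, and a script built from it would carry the presupposition.

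A reader might infer more, and the protocol does not support these stronger readings:

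- **That the screening answers are primed.** Everyone called had already reported pain at baseline. Eligibility rests on a neutral frequency question, and neither screening item mentions depression or BA.
- **That the interviews are led.** The topic guide is not shown, and it is to be piloted with the first two participants and amended if required.
- **That the themes will tilt towards pain as a barrier to BA.** 'Impacted' names no direction.
- **That the whole conclusion rests on about 10 people.** Ten is the initial round, and the combined conclusion also draws on the quantitative study, which this invitation cannot affect.

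**Conclusion.** The point holds as an inexpensive improvement, not as shown bias. Two facts are established: the described invitation takes for granted an effect that the aim leaves open, and it comes before the screen, at a step where losses would be neither seen nor made good. That people who feel pain made no difference may be under-represented is a plausible inference. It rests on two assumptions: that the call follows the described wording, and that this wording deters such people more than others. The protocol confirms neither, and no percentage can be put on the effect.

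**What to change.** In the recruitment paragraph, and in any call script based on it, describe the invitation as asking about the person's experience of BA Support and *whether, and if so how, pain made a difference to their mood or to that support*. Add that people who feel it made no difference are equally wanted. This wording serves both the 'if' in the aim and the 'how' in the knowledge gap, and it discloses the purpose just as fully.

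The same sentence needs a small edit in any case: it invites feedback on the sub-study, in which the person has not yet taken part.

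The cost is rewording one sentence, one added statement, and matching changes to any script. No extra participants, data or staff are needed. No change to the topic guide is proposed, because it is not shown.
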